8.5.1. Time Period and Frequency for Collecting AE and SAE Information

After informed consent but prior to initiation of study drug, the following types of events should be reported: all AEs and SAEs related to protocol-mandated procedures.

Medical occurrences (events considered not related to protocol-mandated procedures) that begin before the start of study drug but after obtaining informed consent will be recorded on the Medical History/Current Medical Conditions section of the eCRF not the AE section.

All AEs and SAEs, regardless of cause or relationship, will be collected from the start of study drug through the Follow-Up visit, at every study visit, as specified in the Schedule of Activities (Section 1.1).

All SAEs will be recorded and reported to the Sponsor or designee immediately and under no circumstance should this exceed 24 hours, as indicated in Appendix 6. The Investigator will submit any updated SAE data to the Sponsor within 24 hours of it being available.

Investigators are not obligated to actively seek reports of AEs or SAEs after conclusion of the study participation. However, if the Investigator learns of any SAE, including a death, at any time after a patient has been discharged from the study, and he/she considers the event to be reasonably related to the study drug or study participation, the Investigator must promptly notify the Sponsor.

8.5.2. Method of Detecting AEs and SAEs

The method of recording, evaluating, and assessing causality of AEs and SAEs and the procedures for completing and transmitting SAE reports are provided in Appendix 6.

Care will be taken not to introduce bias when detecting AEs and/or SAEs. Open-ended and non-leading verbal questioning of the patient is the preferred method to inquire about AE occurrences.

8.5.3. Follow-up of AEs and SAEs

After the initial AE and/or SAE report, the Investigator is required to proactively follow each patient at subsequent visits/contacts. All SAEs will be followed until resolution, stabilization, the event is otherwise explained, or the patient is lost to follow-up (as defined in Section 7.3). Further information on follow-up procedures is provided in Appendix 6.

8.5.4. Regulatory Reporting Requirements for SAEs

Prompt notification by the Investigator to the Sponsor of a SAE is essential so that legal obligations and ethical responsibilities towards the safety of patients and the safety of a study drug under clinical investigation can be met.

The Sponsor has a legal responsibility to notify both the local regulatory authority and other regulatory agencies about the safety of a study drug under clinical investigation. The Sponsor will comply with country-specific regulatory requirements relating to safety reporting to the regulatory authority, IRB/IEC, and Investigators.

Investigator safety reports must be prepared for SUSARs according to local regulatory requirements and sponsor policy and forwarded to Investigators as necessary.

An Investigator who receives an investigator safety report describing a SAE or other specific safety information (e.g., summary or listing of SAEs) from the sponsor will review and then file it along with the Investigator's Brochure and will notify the IRB/IEC, if appropriate according to local requirements.

8.5.5. Pregnancy

Details of all pregnancies in female patients and female partners of male patients will be collected after the start of study drug until 30 days following the last dose of the study drug.

If a pregnancy is reported, the Investigator should inform the Sponsor within 24 hours of learning of the pregnancy and should follow the procedures outlined in Appendix 6 and Appendix 7.

Abnormal pregnancy outcomes (eg, spontaneous abortion, fetal death, stillbirth, congenital anomalies, ectopic pregnancy) are considered SAEs.

8.5.6. Assessment of Pruritus

For patients who report AEs consistent with pruritus, photographs of the affected area(s) will be taken at the discretion of the Investigator (eg, if there are visible skin lesions; photos that would identify the patient, ie, of the entire face, will be avoided). A qualified staff member will administer the Pruritus Numerical Rating Scale (Appendix 8) at each study visit when pruritus is reported or noted as ongoing. If pruritus is reported (either ongoing or at any time since the last visit), the clinical site will provide details on these events in the AE eCRF page.

The Investigator will be asked to provide an assessment of the severity of the AE using the NCI CTCAE v5.0 categories for pruritus as follows:

- Grade 1: Mild or localized; topical intervention indicated.
- Grade 2: Widespread and intermittent; skin changes from scratching (eg, edema, papulation, excoriations, lichenification, oozing/crusts); oral intervention indicated; limiting instrumental activities of daily living (ADL).
- Grade 3: Widespread and constant; limiting self-care, ADL, or sleep; systemic corticosteroid or immunosuppressive therapy indicated.

Protocol TERNCB-2002 Terns, Inc.

For Grade 3 cases, follow up by telephone contact or in person visit should occur within 3 days or at the discretion of the Investigator. Additional follow up may take place until symptoms improve. Refer to Section 7 for additional information on study drug discontinuation and study stopping rules.

8.6. Treatment of Overdose

Overdose with TERN-501 monotherapy, TERN-101 monotherapy, or TERN-501+TERN-101 has not been reported. Neither the effect of overdose nor antidote are known. The maximum amount of TERN-101 that can be safely administered in a single dose has not been determined. The highest single dose of TERN-101 in clinical studies was 25 mg in the tablet formulation and 600 mg in the capsule formulation (see Section 2.2.2.2) and the highest single dose of TERN-501 in clinical studies was 60 mg. The highest single dose of TERN-101 was 3mg and 15mg respectively. Patients who receive higher than the protocol-defined dose should be carefully monitored for AEs, and the quantity of the excess dose and duration of excess dose should be documented in the eCRF; the Medical Monitor should be notified immediately. Refer to Appendix 6 for additional information on AE reporting.

In an instance in which a patient receives higher than the protocol-defined dose, decisions regarding any future dosing of study drug will be made by the Investigator in consultation with the Sponsor based on the clinical evaluation of the patient.

8.7. Medical Resource Utilization and Health Economics

Medical resource utilization and health economics parameters are not evaluated in this study.

9. Statistical Considerations

9.1. Statistical Hypotheses

The primary statistical analysis will test whether the mean relative change from baseline in MRI-PDFF is (H₁) or is not (H₀) different between placebo and TERN-501 monotherapy. Secondary statistical analyses will test whether the mean relative change from baseline in MRI-PDFF is (H₁) or is not (H₀) different between placebo and TERN-501+TERN-101. Similarly, statistical analyses of cT1 will test whether the mean change from baseline is (H₁) or is not (H₀) different between placebo and TERN-501 monotherapy and between placebo and TERN-501+TERN-101. In addition, exploratory analyses will evaluate all pairwise comparisons between the different TERN-501 doses and of TERN-101 compared to placebo and will be considered nominal and descriptive.

9.2. Sample Size Determination

Approximately 140 patients will be randomized into one of the 7 groups (n=20 each) to detect a clinically meaningful difference in the primary endpoint and secondary endpoints of MRI-PDFF relative reduction at Week 12 and secondary endpoints of cT1 reduction at Week 12 between placebo and TERN-501 monotherapy and separately between placebo and TERN-501+TERN-101.

Power was estimated based on published literature for THR- β agonist resmetirom (to estimate TERN-501 effect) and clinical data for TERN-101 (Study TERN101-2001). Assuming a pooled standard deviation of 22% (Study TERN101-2001 final analysis), with a two-sided alpha of 0.05, a mean relative reduction difference in MRI-PDFF at Week 12 of

- 23% between placebo (n=20) and TERN-501 monotherapy (n=20) will provide approximately 90% power (Harrison 2019).
- 36% between placebo (n=20) and TERN-501+TERN-101 (n=20) will provide >90% power, based on placebo treatment effect from resmetirom (Harrison 2019) and sum of treatment effects from resmetirom (to estimate TERN-501 effect) and minimum treatment effect for TERN-101 (Study TERN101-2001), assuming an additive effect of the two agents in combination.

Assuming a pooled standard deviation of 82 msec (Study TERN101-2001 final analysis), with a two-sided alpha of 0.05, a mean reduction difference in cT1 at Week 12

- of 77 msec between placebo (n=20) and TERN-501 monotherapy (n=20) will provide approximately 82% power (Harrison 2018).
- 134 msec between placebo (n=20) and TERN-501+TERN-101 (n=20) will provide >90% power, based on placebo treatment effect from resmetirom (Harrison 2019) and sum of treatment effects from resmetirom (to estimate TERN-501 effect) and minimum treatment effect for TERN-101 (Study TERN101-2001), assuming an additive effect of the two agents in combination.

Patients who are randomized but do not receive study drug for any reason may be replaced. In addition, patients who discontinue treatment early for reasons other than safety (i.e., withdrawal

Protocol TERNCB-2002 Terns, Inc.

of consent, lost to follow-up, patient relocated, etc.) may also be replaced, at the Sponsor's discretion. Replacement patients will receive the same treatment assignment as the patient that discontinued treatment early.

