6.4. Measures to Minimize Bias: Randomization and Blinding

Patients will be randomized to 1 of 3 dose levels TERN-501 monotherapy, 1 of 2 dose levels TERN-501+TERN-101, 10mg TERN-101 monotherapy, or placebo using an Interactive Web Response System (IWRS). Before the study is initiated, the log-in information and directions for the IWRS will be provided to each site.

Approximately 140 patients will be randomized equally into one of the 7 treatment groups to receive once daily orally administered TERN-501 1 mg (n=20), TERN-501 3 mg (n=20), TERN-501 6 mg (n=20), TERN-501 3 mg+TERN-101 10 mg (n=20), TERN-501 6 mg+TERN-101 10 mg (n=20), TERN-101 10 mg (n=20), or matching placebo (n=20).

All personnel directly involved in the conduct of the study (i.e., Investigators, patients, all study personnel, Medical Monitor, and the Sponsor) will remain blinded to each patient's assigned dose group throughout the course of the study. Individuals in IP packaging and labeling who have Unblinded Inventory Manager role in the IXRS system for study drug inventory management will remain unblinded. Individuals at the PK bioanalytical laboratory will remain unblinded to facilitate sample processing, as placebo samples will not be analyzed for PK. Study drug will be dispensed at the study visits as summarized in Schedule of Activities. Returned study drug should not be re-dispensed to patients.

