9.3. Analysis Sets

The following analysis sets are defined:

Analysis Sets	Description
Screened	All patients who sign the ICF
Randomized	All patients who are randomized into any one of treatment groups. Treatment assignment will be based on the randomized treatment.
Pharmacokinetic (PK)	All randomized patients who received at least 1 dose of TERN-501 and/or TERN-101 and have evaluable PK data. Treatment assignment will be based on the treatment actually received.
Pharmacodynamic (PD)	All randomized patients who received at least 1 dose of study drug (TERN-501, TERN-101, or placebo) and for whom PD markers can be evaluated. Treatment assignment will be based on the treatment actually received.
PK/PD sub-study	All patients who consented to and participated in the PK/PD sub-study and received at least 1 dose of study drug (TERN-501, TERN-101, or placebo). Treatment assignment will be based on the treatment actually received.
Safety	All patients who received at least 1 dose of study drug. Treatment assignment will be based on the treatment actually received.
Efficacy	All randomized patients who received at least 1 dose of study drug. Treatment assignment will be based on the randomized treatment.

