9.4.1. General Considerations

For continuous data, summary statistics will include the number of non-missing observations (n), arithmetic mean, arithmetic standard deviation, median, 25th percentile (Q1), 75th percentile (Q3), minimum, and maximum. For log-normal data (eg, the PK parameters: AUCs and maximum observed concentration [C_{max}]), the geometric mean and geometric coefficient of

variation (CV%) will also be presented. For categorical data, frequency counts and percentages will be presented.

The baseline value for statistical analyses of quantitative laboratory parameters is defined as the mean of all available evaluations, including any unscheduled or repeat assessments, prior to the first administration of study drug. Otherwise, the baseline value is defined to be the latest assessment value prior to the first administration of study drug, unless specified in the SAP.

Missing values will not be imputed for primary analyses. However, sensitivity analyses will be conducted to evaluate the effect of missing data. Further details will be specified in the SAP.

No adjustments for multiplicity will be made.

Data analysis will be performed using SAS[®] Version 9.4 or higher. Noncompartmental PK parameters will be estimated from individual plasma concentration data using Phoenix[®] WinNonlin[®].

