7.2. Handling of Dropouts or Missing Data

Primary analyses will be based on observed data. For the primary endpoint, a sensitivity analysis will be conducted for patients who do not complete the Week 12 visit, where the last on-treatment value, including any values collected at unscheduled visits, will be carried forward (LOCF) and used for Week 12.

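### If the sponsor uses its replacement option, the new patient inherits the departed patient's arm instead of being randomised, and no planned analysis identifies such patients.

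*Protocol*

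**What the plan says.** Protocol 9.2, also in the synopsis and in SAP 2.3, allows two kinds of replacement.

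- Never-dosed patients: "Patients who are randomized but do not receive study drug for any reason may be replaced".
- Early discontinuers: "patients who discontinue treatment early for reasons other than safety" "may also be replaced, at the Sponsor's discretion".

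For the second kind the arm is fixed: "Replacement patients will receive the same treatment assignment as the patient that discontinued treatment early". No cap, cut-off date or separate randomisation list is given. The arm for a patient who replaces someone never dosed is not expressly stated.

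Protocol 9.3 defines the Efficacy set as "All randomized patients who received at least 1 dose of study drug. Treatment assignment will be based on the randomized treatment". SAP Section 4 has the same definition. Neither says whether a replacement counts as randomised. On missing data, Protocol 9.4.1 says "Missing values will not be imputed for primary analyses" and SAP 7.2 says "Primary analyses will be based on observed data". LOCF is the only missing-data sensitivity analysis planned (SAP 7.2 and 7.8).

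Protocol 6.4 says that the sponsor, sites and patients "will remain blinded to each patient's assigned dose group throughout the course of the study".

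**The concern.** Randomisation justifies comparing arms because chance alone decides who is in each. Under this rule a replacement's arm is decided by which earlier patient left. An arm that loses more patients is refilled with more late enrollees, so its make-up comes to depend on events after randomisation. If late enrollees respond differently, for example because sites, season or screening practice have shifted, that difference is carried into the treatment contrast.

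The primary comparison has only 20 patients per arm, so two or three such patients form a visible share of an arm. As planned, a reader of the report could not tell how many there were or whether the primary result depends on them.

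**Working it through.** **1. The plan's own figure.** Protocol 9.2 gives SD 22 points, difference 23, 20 per arm, two-sided alpha 0.05 and about 90% power. The standardised difference is 23 / (22 × √(1/20 + 1/20)) = 23 / 6.957 = 3.306. The normal approximation gives Φ(3.306 − 1.960) = 91.1%; the noncentral t with 38 df gives 89.6%. The stated power reproduces, so the sample-size arithmetic is not in question.

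**2. Can a replacement reach the primary analysis?**
- Replacement is triggered by stopping treatment. Protocol 7.1.2 keeps such patients in follow-up, but SAP 3.8.1 treats any assessment more than 14 days from the last dose as unscheduled. An early discontinuer's Week 12 scan is then not a Week 12 value, even if it was done.
- With observed data and no imputation, that patient is absent from the Week 12 ANCOVA while the same-arm replacement can be present.
- The Per Protocol set (SAP Section 4) requires study completion, so it drops those who leave and can admit their replacements. It offers no check.
- The subgroups (SAP Section 5) and disposition items (SAP 6.1) do not identify replacements.

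**3. How many?** The documents give no withdrawal rate, so 10-15% is assumed, with every such patient replaced. Then 140 × 0.10 = 14 and 140 × 0.15 = 21, or 20 × 0.10 = 2 to 20 × 0.15 = 3 per arm. For 5-20% the range is 7 to 28 of 140. All are upper figures for the assumed rate, because replacement is optional. The lower end is 0.

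**4. What bias follows?** Let Δ be the mean outcome difference between replacements and earlier patients, and s the share of an arm's observed Week 12 values that come from replacements. Then bias ≈ Δ × (s_active − s_placebo). With one replacement per departure, and replacements leaving at the same rate d without being replaced again, s = d(1 − d) / [(1 − d) + d(1 − d)] = d / (1 + d).
- Assume d = 20% on active and 5% on placebo, with Δ = −11 points (half an SD; negative favours active).
- Same-arm rule: s_active = 0.20/1.20 = 0.167 and s_placebo = 0.05/1.05 = 0.048. Bias ≈ −11 × 0.119 = −1.3 points.
- Fresh randomisation of the same five expected extra patients over two arms: 2.5 / 22.5 = 0.111 in each arm, so bias is 0.
- If d is equal across arms, or Δ = 0, the same-arm rule adds no bias.

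**5. Simulation under no treatment effect.** Two arms of 20, SD 22, t-test, 8,000 runs per setting. The Monte Carlo standard error is about √(0.05 × 0.95/8000) = 0.24 percentage points for type I error. Entries are bias in points and type I error. All dropout inputs are assumptions; the outcome link is a correlation of 0.5.

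| Dropout (placebo / active) | Outcome link | Δ | No replacement | Same arm | Randomised |
|---|---|---|---|---|---|
| 5% / 20% | none | 0 | 0.15; 5.3% | 0.05; 5.1% | 0.19; 4.8% |
| 5% / 20% | none | −11 | 0.03; 5.0% | −1.30; 5.6% | −0.07; 4.8% |
| 5% / 20% | 0.5 | 0 | −2.84; 6.8% | −2.68; 6.7% | −2.71; 6.6% |
| 5% / 20% | 0.5 | −11 | −2.73; 6.2% | −3.81; 8.4% | −2.63; 6.2% |

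With 10% dropout in both arms, every setting gave bias within 0.2 points and type I error between 4.5% and 5.4%. In the last row the rule itself adds −3.81 − (−2.63) = −1.18 points. The other 2.63/3.81 = 69% is present even with randomised replacement.

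**6. Is a sensitivity analysis without replacements worth running?** With 18 or 17 patients per arm (10% or 15% removed), primary power by noncentral t is 86.1% or 84.0%.

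**The case against.** The case against acting is substantial.

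- **The rule is permissive.** A reader might infer that part of the primary comparison is certain to be non-randomised. The text does not support that; if the option is never used, nothing is affected.
- **Membership is inferred.** Neither document says that replacements are in the Efficacy set. It is the natural reading, since otherwise replacement would add nothing to the primary analysis, but the firm finding is that the SAP is silent.
- **The departed patient is not necessarily lost.** A reader might infer that each replacement simply substitutes for the earlier patient. No text removes that patient from the Efficacy set. A scan on Days 71-99 and within 14 days of the last dose maps to Week 12, an early-termination MRI is possible after at least 4 weeks of dosing, and LOCF brings back the last on-treatment value. Both patients can contribute.
- **Deliberate selection is hard.** The sponsor and sites are blinded, and safety discontinuations after dosing are not replaceable, so one obvious arm-dependent kind of departure is not refilled.
- **Withdrawal is already reported by arm.** SAP 6.1 tabulates early discontinuation and reasons by treatment group, so imbalance would be visible.

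All of this limits size and certainty. None of it makes the replacement's allocation random, and none lets a reader separate these patients. A further objection is that dropping replacement costs power: cT1 power would fall from about 82% to 78-76% at 10-15% dropout. That applies to having no replacement at all. Randomising the same number of extra patients does not reduce total enrolment.

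**Conclusion.** The point stands as a conditional weakness that is cheap to remove. If the option is used, a replacement's arm depends on an earlier patient's departure, such patients most naturally enter the primary ANCOVA, and no planned analysis shows their influence.

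The number is unknown: from 0 up to about 14 to 21 of 140 under assumed 10-15% withdrawal with full replacement. Bias needs two conditions together, namely unequal withdrawal between arms and replacements who differ from those they replace. With 20% against 5% withdrawal and a half-SD difference it is about −1.3 points (type I error 5.6%), or 1.3/23 = 6% of the planned effect.

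A reader might go further and conclude that the primary result would be seriously biased, or that the 8.4% error rate in the worst setting is due to this rule. The check does not support either. Most of the bias in that setting comes from outcome-dependent dropout under an observed-data analysis, and it remains at −2.6 to −2.7 points with randomised replacement or with none.

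**What to change.** 1. **Allocation.** Change the sentence in the Protocol synopsis, Protocol 9.2 and SAP 2.3 so that any replacement receives the next number on the IWRS randomisation list, with the same number of extra patients. Say that this also covers replacements for never-dosed patients, whose arm is now unstated. The cost is a protocol wording change, slightly unequal arms and, if the study is under way, an amendment that needs IRB/IEC approval (Protocol 10.1). If enrolment has closed, this part no longer applies.
2. **Analysis, in any case, before unblinding.** State in SAP Section 4 that replacements belong to the Efficacy set and that the patients they replace stay in it. Flag replacements and count them by arm in the disposition table (SAP 6.1). Add to SAP 7.2 and 7.8 one sensitivity ANCOVA of the primary endpoint that excludes patients assigned by the same-arm rule. The cost is one flag, one table row and one model run.

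Neither part addresses bias from outcome-dependent dropout in the observed-data analysis; that needs separate treatment.

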9.3. Analysis Sets

The following analysis sets are defined:

Analysis Sets	Description
Screened	All patients who sign the ICF
Randomized	All patients who are randomized into any one of treatment groups. Treatment assignment will be based on the randomized treatment.
Pharmacokinetic (PK)	All randomized patients who received at least 1 dose of TERN-501 and/or TERN-101 and have evaluable PK data. Treatment assignment will be based on the treatment actually received.
Pharmacodynamic (PD)	All randomized patients who received at least 1 dose of study drug (TERN-501, TERN-101, or placebo) and for whom PD markers can be evaluated. Treatment assignment will be based on the treatment actually received.
PK/PD sub-study	All patients who consented to and participated in the PK/PD sub-study and received at least 1 dose of study drug (TERN-501, TERN-101, or placebo). Treatment assignment will be based on the treatment actually received.
Safety	All patients who received at least 1 dose of study drug. Treatment assignment will be based on the treatment actually received.
Efficacy	All randomized patients who received at least 1 dose of study drug. Treatment assignment will be based on the randomized treatment.

